11.1.3 Methods for Evaluation of Measurable Disease

All measurements should be taken and recorded in metric notation using a ruler or calipers. All baseline evaluations should be performed as closely as possible to the beginning of treatment and never more than 4 weeks before the beginning of the treatment.

The same method of assessment and the same technique should be used to characterize each identified and reported lesion at baseline and during follow-up. Imaging-based evaluation is preferred to evaluation by clinical examination unless the lesion(s) being followed cannot be imaged but are assessable by clinical exam.

Chest x-ray: Lesions on chest x-ray are acceptable as measurable lesions when they are clearly defined and surrounded by aerated lung. However, CT is preferable.

Conventional CT and MRI: This guideline has defined measurability of lesions on CT scan based on the assumption that CT slice thickness is 5 mm or less. If CT scans have slice thickness greater than 5 mm, the minimum size for a measurable lesion should be twice the slice thickness. MRI is also acceptable in certain situations (*e.g.* for body scans).

Use of MRI remains a complex issue. MRI has excellent contrast, spatial, and temporal resolution; however, there are many image acquisition variables involved in MRI, which greatly impact image quality, lesion conspicuity, and measurement. Furthermore, the availability of MRI is variable globally. As with CT, if an MRI is performed, the technical specifications of the scanning sequences used should be optimized for the evaluation of the type and site of disease. Furthermore, as with CT, the modality used at follow-up should be the same as was used at baseline and the lesions should be measured/assessed on the same pulse sequence. It is beyond the scope of the RECIST guidelines to prescribe specific MRI pulse sequence parameters for all scanners, body parts, and diseases. Ideally, the same type of scanner should be used and the image acquisition protocol should be followed as closely as possible to prior scans. Body scans should be performed with breath-hold scanning techniques, if possible.

11.1.4 Response Criteria

11.1.4.1 Evaluation of Target Lesions

| Complete Response (CR): | Disappearance of all target lesions. Any pathological lymph nodes (whether target or non-target) must have reduction in short axis to < 10 mm. |
|---------------------------|---|
| Partial Response (PR): | At least a 30% decrease in the sum of the diameters of target lesions, taking as reference the baseline sum diameters. |
| Progressive Disease (PD): | At least a 20% increase in the sum of the diameters of target lesions, taking as |

| | reference the smallest sum on study (this includes the baseline sum if that is the smallest on study). In addition to the relative increase of 20%, the sum must also demonstrate an absolute increase of at least 5 mm. (Note: the appearance of one or more new lesions is also considered progressions). |
|----------------------|--|
| Stable Disease (SD): | Neither sufficient shrinkage to qualify for PR nor sufficient increase to qualify for PD, taking as reference the smallest sum diameters while on study. |

11.1.4.2 Evaluation of Non-Target Lesions

| Complete Response (CR) : | Disappearance of all non-target lesions. All lymph nodes must be non-pathological in size (<10 mm short axis). |
|---------------------------------|--|
| Non-CR/Non-PD: | Persistence of one or more non-target lesion(s) and/or maintenance of tumor marker level above the normal limits. |
| Progressive Disease (PD): | Unequivocal progression (see comments below of existing non-target lesions. (Note: the appearance of one or more new lesions is also considered progression). |
| | Note: When the patient also has measurable disease. In this setting, to achieve 'unequivocal progression' on the basis of the non-target disease, there must be an overall level of substantial worsening in non-target disease such that, even in presence of SD or PR in target disease, the overall tumor burden has increased sufficiently to merit discontinuation of therapy. A modest 'increase' in the size of one or more non-target lesions is usually not sufficient to quality for unequivocal progression status. The designation of overall progression solely on the basis of change in non-target disease in the face of |

| Target Lesions | Non-Target Lesions | New Lesions | Overall Response | | | |
|---|-----------------------------|-------------|---------------------|--|--|--|
| CR | CR | No | CR | | | |
| CR | Non-CR/ Non-PD | No | PR | | | |
| CR | Not evaluated | No | PR | | | |
| PR | Non-PD or not all evaluated | No | PR | | | |
| SD | Non-PD or not all evaluated | No | SD | | | |
| Not all evaluated | Non-PD | No | NE | | | |
| PD | Any | Yes or No | PD | | | |
| Any | PD* | Yes or No | PD | | | |
| Any | Any | Yes | PD | | | |
| CR = Complete Response, PR = Partial Response, SD = Stable Disease, PD = Progressive Disease, and NE = inevaluable * In exceptional circumstances, unequivocal progression in non-target lesions may be accepted as disease progression. | | | | | | |

11.1.4.3 Evaluation of Tumor Response

11.1.4.4 Best Overall Response when confirmation of CR and PR required

The best overall response is the best response recorded from the start of the study treatment until disease progression/recurrence (taking as reference for progressive disease the smallest measurements recorded since the treatment started). The patient's best overall response assignment will depend on the achievement of both measurement and confirmation criteria.

| Overall response First time point | Overall Response Subsequent time point | Best Overall Response | |
|---|---|---|--|
| CR | CR | CR | |
| CR | PR | SD, PD or PR ^a | |
| CR | SD | SD provided minimum criteria for SD duration met, otherwise PD | |
| CR | PD | SD provided minimum criteria for SD duration met, otherwise PD | |
| CR | NE | SD provided minimum criteria for SD duration met, otherwise NE | |
| PR | CR | PR | |
| PR | PR | PR | |
| PR | SD | SD | |
| PR | PD | SD provided minimum criteria for SD duration met, otherwise PD | |
| PR | NE | SD provided minimum criteria for SD duration met, otherwise NE | |
| NE | NE | NE | |

CR = Complete Response, PR = Partial Response, SD = Stable Disease, PD = Progressive Disease, and NE = Inevaluable

^a If a CR is truly met at first time point, then any disease seen at a subsequent time point, even disease meeting PR criteria relative to baseline, makes the disease PD at that point (since disease must have reappeared after CR). Best response would depend on whether minimum duration for SD was met. However, sometimes 'CR' may be claimed when subsequent scans suggest small lesions were likely still present and in fact the patient had PR, not CR at the first time point. Under these circumstances, the original CR should be changed to PR and the best response is PR.

11.1.5 Duration of Response

Duration of overall response: The duration of overall response is measured from the time measurement criteria are met for CR or PR (whichever is first recorded) until the first date that recurrent or progressive disease is objectively documented (taking as reference for progressive disease the smallest measurements recorded since the treatment started). The duration of overall CR is measured from the time measurement criteria are first met for CR until the first date that progressive disease is objectively documented.

Duration of stable disease: Stable disease is measured from the start of the treatment until the criteria for progression are met, taking as reference the smallest measurements recorded since the treatment started, including the baseline measurements.

11.1.6 Progression-Free Survival

Progression-Free Survival is defined as the duration of time from start of treatment to time of progression or death, whichever occurs first.

11.1.7 Response Review

All responses will be investigator assessed. Responses may also be reviewed by an expert(s) independent of the study at the study's completion.

11.1.8 Definition of Tumor Response Using irRC

The sum of the products of diameters (SPD) at tumor assessment using the immune-related response criteria (irRC) for progressive disease incorporates the contribution of new measurable lesions. Each net percentage change in tumor burden per assessment using irRC criteria accounts for the size and growth kinetics of both old and new lesions as they appear.

11.1.8.1. Definition of Index Lesions Response Using irRC

- irComplete Response (irCR): Complete disappearance of all index lesions. This category encompasses exactly the same patients as "CR" by the modified WHO (mWHO) criteria.
- irPartial Response (irPR): Decrease, relative to baseline, of 50% or greater in the sum of the products of the two largest perpendicular diameters of all index and all new measurable lesions (i.e., Percentage Change in Tumor Burden). Note: the appearance of new measurable lesions is factored into the overall tumor burden, but does not automatically qualify as progressive disease until the SPD increases by ≥25% when compared to SPD at nadir.

- irStable Disease (irSD): Does not meet criteria for irCR or irPR, in the absence of progressive disease.
- irProgressive Disease (irPD): At least 25% increase Percentage Change in Tumor Burden (i.e., taking sum of the products of all index lesions and any new lesions) when compared to SPD at nadir.

11.1.8.2 Definition of Non-Index Lesions Response Using irRC

- irComplete Response (irCR): Complete disappearance of all nonindex lesions. This category encompasses exactly the same patients as "CR" by the mWHO criteria.
- irPartial Response (irPR) or irStable Disease (irSD): non-index lesion(s) are not considered in the definition of PR, these terms do not apply.
- irProgressive Disease (irPD): Increases in number or size of nonindex lesion(s) does not constitute progressive disease unless/until the Percentage Change in Tumor Burden increases by 25% (i.e., the SPD at nadir of the index lesions increases by the required amount).

11.1.8.3 Impact of New Lesions on irRC

New lesions in and by themselves do not qualify as progressive disease. However, the contribution of new measurable lesions to total tumor burden is included in the SPD which in turn feeds into the irRC criteria for tumor response. Therefore, new nonmeasurable lesions will not discontinue any patient from the study.

11.1.8.4 Definition of Overall Response Using irRC

Overall response using irRC will be based on these criteria:

- **Immune-Related Complete Response (irCR):** Complete disappearance of all tumor lesions (index and nonindex together with no new measurable/unmeasurable lesions) for at least 4 weeks from the date of documentation of complete response.
- Immune-Related Partial Response (irPR): The sum of the products of the two largest perpendicular diameters of all index lesions is measured and captured as the SPD baseline. At each

subsequent tumor assessment, the sum of the products of the two largest perpendicular diameters of all index lesions and of new measurable lesions are added together to provide the Immune Response Sum of Product Diameters (irSPD). A decrease, relative to baseline of the irSPD compared to the previous SPD baseline, of 50% or greater is considered an immune Partial Response (irPR).

- Immune-Related Stable Disease (irSD): irSD is defined as the failure to meet criteria for immune complete response or immune partial response, in the absence of progressive disease.
- Immune-Related Progressive Disease (irPD): It is recommended in difficult cases to confirm PD by serial imaging. Any of the following will constitute progressive disease:
 - At least 25% increase in the sum of the products of all index lesions over baseline SPD calculated for the index lesions.
 - At least a 25% increase in the sum of the products of all index lesions and new measurable lesions (irSPD) over the baseline SPD calculated for the index lesions.

| Index Lesion Definition | Non-Index Lesion Definition | New Measurable Lesions | New Unmeasurable Lesions | Percent change in tumor burden (including measurable new lesions when present) | Overall irRC Response |
|-------------------------------|-----------------------------------|------------------------------|--------------------------------|---|-----------------------------|
| Complete Response | Complete Response | No | No | -100% | irCR |
| Partial Response | Any | Any | Any | ≥ -50% | irPR |
| Stable Disease | Any | Any | Any | <-50% to <+25% | irSD |
| Progressive Disease | Any | Any | Any | ≥+25% | irPD |

Table 8: Immune-Related Response Criteria Definitions

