11. MEASUREMENT OF EFFECT

11.1 Antitumor Effect – Solid Tumors

For the purposes of this study, patients should be evaluated for response initially after first 8 weeks on study and then every 12 weeks.

Response and progression will be evaluated in this study using the new international criteria proposed by the revised Response Evaluation Criteria in Solid Tumors (RECIST) guideline (version 1.1) [*Eur J Ca* 45:228-247, 2009]. Changes in the largest diameter (unidimensional measurement) of the tumor lesions and the shortest diameter in the case of malignant lymph nodes are used in the RECIST criteria.

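### Immune-related progression (irPD) is measured from nadir in sections 11.1.8.1 and 11.1.8.2 but from baseline in 11.1.8.4, and no rule says which governs

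*Combined protocol and SAP*

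**What the plan says.** Section 11.1.8 of the combined protocol and SAP defines irRC response by layer: index lesions (11.1.8.1), non-index lesions (11.1.8.2), new lesions (11.1.8.3) and overall response (11.1.8.4, which includes Table 8).

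**Nadir as reference.** The note under irPR in 11.1.8.1 says that the appearance of new measurable lesions "does not automatically qualify as progressive disease until the SPD increases by ≥25% when compared to SPD at nadir". The irPD entry in that section again asks for a 25% rise, "taking sum of the products of all index lesions and any new lesions) when compared to SPD at nadir". Section 11.1.8.2 ties progression in non-index lesions to the same yardstick: "the SPD at nadir of the index lesions increases by the required amount".

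**Baseline as reference.** Section 11.1.8.4 opens with "Overall response using irRC will be based on these criteria". Its first irPD criterion is "At least 25% increase in the sum of the products of all index lesions over baseline SPD calculated for the index lesions". Its second applies the same 25% to index lesions plus "new measurable lesions (irSPD) over the baseline SPD calculated for the index lesions".

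**Table 8.** Each row combines an index-lesion category, non-index and new-lesion columns, and a percent change in tumor burden. The percent column's heading names neither baseline nor nadir. It prints irPR as `≥ -50%`, irSD as `<-50% to <+25%` and irPD as `≥+25%`. The text of 11.1.8.1 and 11.1.8.4 sets irPR at a fall of at least 50% from baseline.

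The irRC response rate is the third secondary objective (1.2). Sections 13.3 and 13.4.2 also list irRC as secondary.

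**The concern.** Nadir and baseline are different yardsticks as soon as the tumor burden has shrunk at all. A patient who shrinks and then regrows can be irPD under one part of section 11.1.8 and not under another, on the same scan and the same measurements. Two analysts following the document could assign different irRC categories and different irPD dates.

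A second gap follows from the first. Section 11.1.8 does not say which category applies if a scan meets both irPR and irPD, or whether an irPR reached after an irPD counts as a response. Under the nadir rule both situations can arise, so the ambiguity could reach the irRC response rate as well as the progression category.

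**Working it through.** The plan gives no sample size, power or event figure that depends on irRC, so there is no stated figure to reproduce. The check applies each written rule to the same measurements.

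**Inputs.** The 25% rise and its two references come from 11.1.8.1, 11.1.8.2 and 11.1.8.4. The 50% fall from baseline for irPR comes from 11.1.8.1 and 11.1.8.4. Scan times come from 11.1: "patients should be evaluated for response initially after first 8 weeks on study and then every 12 weeks", that is weeks 8, 20 and 32. All SPD values below are assumed for illustration. Baseline is set to 100, and SPD means index lesions plus any new measurable lesions.

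**Step 1: where the rules disagree.** Let the nadir be f times baseline, with f at most 1.
- Nadir rule: irPD when SPD ≥ 1.25 × f × baseline.
- Baseline rule: irPD when SPD ≥ 1.25 × baseline.
- Disagreement: from 1.25f to just under 1.25 times baseline, a width of 1.25(1 − f).

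| f | Nadir rule triggers at | Baseline rule triggers at | Width of disagreement (points of baseline) |
|---|---|---|---|
| 0.9 | 112.5 | 125 | 12.5 |
| 0.8 | 100 | 125 | 25 |
| 0.7 | 87.5 | 125 | 37.5 |
| 0.6 | 75 | 125 | 50 |

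The rules agree only if f = 1.

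**Step 2: effect on the irPD date.** Take SPDs of 100 at baseline, then 70, 90 and 130 at weeks 8, 20 and 32.
- Week 20: 90/70 − 1 = +28.6% from nadir, so irPD by the nadir rule. 90/100 − 1 = −10% from baseline, so irSD by the baseline rule.
- Week 32: 130/100 − 1 = +30% from baseline, so irPD by the baseline rule.
- Difference in date: 32 − 20 = 12 weeks.

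**Step 3: scans that meet both irPR and irPD.** irPR needs SPD ≤ 0.5 × baseline and nadir-based irPD needs SPD ≥ 1.25f × baseline. A band satisfies both when 1.25f < 0.5, that is f < 0.4. With nadir 30 and current 40, the change is 40/100 − 1 = −60% from baseline (irPR) and 40/30 − 1 = +33.3% from nadir (irPD). For f = 0.3 the band is 37.5 to 50. The irSD definition excludes progressive disease; the irPR definition does not.

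**Step 4: a route to the response rate.** Take SPDs of 100, 90, 115 and 45 at baseline and weeks 8, 20 and 32. At week 20, 115/90 − 1 = +27.8% from nadir (irPD) but +15% from baseline (not irPD). At week 32, 45/100 − 1 = −55% (irPR). By the baseline rule the patient is a responder with no earlier irPD. By the nadir rule the irPR follows an irPD, and nothing in 11.1.8 says whether it counts.

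The Step 3 overlap alone is less likely to move the rate. A nadir below 0.4 is already a fall of more than 60%, so that earlier scan meets irPR. The overlap would matter for the rate only if irPR needed a second scan. Section 11.1.8.4 states a minimum duration for irCR but none for irPR.

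**Step 5: does Table 8 resolve it?** Take nadir 80 and current 100: +25% from nadir, 0% from baseline.
- By the 11.1.8.4 criteria: not irPD.
- By Table 8 with percent change from nadir: index category progressive, +25%, so irPD.
- By Table 8 with percent change from baseline: index category progressive by 11.1.8.1, but 0% fails `≥+25%`, so no row fits.

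The table therefore leaves the conflict open.

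**The case against.** The strongest reply is that 11.1.8.4 defines overall response, uses only baseline, and contains Table 8. The table's single percent column includes the −50% cut, which the text measures from baseline. Baseline is thus the more natural reading of that column, and this part of the objection stands. It does not close the gap. The index-lesion category is also an input to the table, and 11.1.8.1 defines progression in that category from nadir while already counting new lesions. The contrast is therefore not simply lesion-level against overall. No section gives precedence.

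A second reply is that no analysis described in 13.3 uses irPD. That also stands, and it limits the weight of the point. A reader might infer that the primary result or PFS is at risk. The documents do not support this: the primary ORR and the 8-of-40 rule (13.1) and PFS (1.2) are by RECIST 1.1.

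A reader might also infer from Table 8's signs that an unchanged tumor would be counted as irPR and that the irRC response rate would be wrong. Read as a signed number on its own, `≥ -50%` does admit 0%. Each row also requires an index-lesion category, however, and 11.1.8.1 requires a fall of at least 50% for a partial response there, so a 0% change cannot satisfy the irPR row. Read as the size of a decrease, the column agrees with the text. The signs are a notation error.

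The opposite inference, that the irPD reference can never affect the irRC response rate because irPR is always measured from baseline, also goes too far, as Step 4 shows.

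**Conclusion.** The contradiction is real and the documents do not resolve it or show which reference was intended. Three statements in 11.1.8.1 and 11.1.8.2 use nadir and both irPD criteria in 11.1.8.4 use baseline. For any patient whose tumor burden has fallen below baseline, SPDs across a band of 1.25(1 − f) times baseline are classified two ways. In the illustration, the irPD date moves by one scan interval, 12 weeks.

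The consequence is limited to irRC categories and irPD dates, and possibly the irRC response rate, depending on how an irPR at or after an irPD is counted. These are secondary outcomes, and the point is minor. The band widths are exact for a given f, but the values of f and the SPD sequences are assumptions. The documents do not allow the number of affected patients to be estimated.

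**What to change.** 1. Reconcile 11.1.8.1, 11.1.8.2, 11.1.8.4 and Table 8 to one irPD reference, and name it in the table.
2. State which category takes precedence when a scan meets both irPR and irPD, and whether an irPR after an irPD counts as a response.
3. Apply the same rules to part-1 and expansion patients, since 13.1 analyzes 10 and 30 of them together in each subtype cohort.
4. As an editorial correction, print Table 8's cut-offs to match the text. irPR: change from baseline ≤ −50%. irSD: none of irCR, irPR or irPD. irPD: ≥ +25% from the stated reference. If nadir is chosen, the irPR and irPD rows overlap, so item 2 is then essential.

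This concerns outcome classification only. The cost is wording in four places, the added precedence rules, and re-deriving irRC categories; no new scans are needed. The re-derivation assumes that follow-up SPDs or lesion measurements were recorded. Section 11.1.8.4 says the baseline value "is measured and captured as the SPD baseline" and that later products are summed at each assessment, but it does not say that the later sums are stored. Section 4.1 says that data for the secondary endpoints go into the eCRFs, which makes this likely; it should be confirmed.

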12. DATA REPORTING / REGULATORY CONSIDERATIONS

12.1 Data Reporting

12.1.1 Method

A final study report describing the outcome of the trial will be created at the end of the study.

12.1.2 Data Safety and Monitoring

SARC is responsible for the Data Safety Monitoring for this trial. SARC Clinical Trials Review Committee convenes monthly and will provide safety oversight for this trial. The purpose of the Clinical Trials Review Committee is to review the status of the on-going SARC studies, which includes, but is not limited to:

- Review of all safety data (Serious Adverse Events reported).
- Review of protocol deviations/violations.
- Review of study progress/accrual.
- Discussion of statistical aspects of all protocols.

The committee is chaired by the SARC Medical Officer, who is responsible for leading the meeting and providing medical oversight. Attendance includes all overall study Principal Investigators on active SARC studies, SARC Research Project Managers, SARC President, and a biostatistician.

Safety oversight for this trial is also supported by the SARC Clinical Research Committee which is made up of senior sarcoma investigators and the SARC President. This committee also convenes monthly. The Medical Officer updates the committee on the ongoing clinical trial status as well as any areas of concern particularly related to safety. This committee provides an additional level of medical oversight for this trial.

